2.2. Study Objectives

2.2.1. Primary Objectives

- **Part 1:** To evaluate the effect of mild (if applicable) and moderate renal impairment on the PK of PF-07321332, following a single oral dose administration of PF-07321332 pharmacokinetically boosted with ritonavir.
- **Part 2:** To evaluate the effect of severe renal impairment on the PK of PF-07321332, following a single oral dose administration of PF-07321332 pharmacokinetically boosted with ritonavir.

2.2.2. Secondary Objectives

- *To evaluate the safety and tolerability of PF-07321332 and ritonavir, following a single oral dose administration of PF-07321332 pharmacokinetically boosted with ritonavir, in participants with renal impairment and in healthy participants with normal renal function.*
- *To characterize additional PK parameters of PF-07321332 following a single oral dose of PF-07321332 pharmacokinetically boosted with ritonavir by renal function.*

3. INTERIM ANALYSES, FINAL ANALYSES AND UNBLINDING

No formal interim analysis will be conducted for this study. However, as this is an open label study, the sponsor may conduct unblinded reviews of the data during the course of the study for the purpose of safety assessment, facilitating PK/PD modeling, and/or supporting clinical development.

Final analysis will follow the official database release. As this will be an open-label study, there is no formal unblinding of the randomization code.

4. HYPOTHESES AND DECISION RULES

4.1. Statistical Hypotheses

No statistical hypothesis will be tested in this study.

4.2. Statistical Decision Rules

There are no statistical decision rules.

5. ANALYSIS SETS

5.1. Pharmacokinetic (PK) Analysis Set

5.1.1. Concentration Analysis Set

The PK concentration population will be defined as all participants treated in whom at least 1 plasma concentration value is reported.

5.1.2. Parameter Analysis Set

The PK parameter analysis population is defined as all participants dosed who have at least 1 of the PK parameters of primary interest.

5.2. Pharmacodynamic Analysis Set

None.

5.3. Safety Analysis Set

All participants randomly assigned to study intervention and who take at least 1 dose of study intervention. Participants will be analyzed according to the product they actually received.

5.4. Other Analysis Sets

None.

5.5. Treatment Misallocations

All analyses will be performed on an “as-treated” basis and will not include data from participants who are randomized but not treated.

If a participant takes a treatment that is not consistent with the treatment they are randomized to, for example takes a treatment out of sequence or takes the same treatment twice, then they will be reported under the treatment that they actually receive for all safety, and PK analyses, where applicable.

5.6. Protocol Deviations

Participants who experience events that may affect their PK profile (eg, lack of compliance with dosing) may be excluded from the PK analysis. At the discretion of the pharmacokineticist a concentration value may also be excluded if the deviation in sampling time is of sufficient concern or if the concentration is anomalous for any other reason.

A full list of protocol deviations will be compiled and reviewed to identify major and minor deviations prior to database closure.

5.6.1. Deviations Assessed Prior to Randomization

At Screening, the investigator will assess participants against the inclusion and exclusion criteria as set out in Sections 5.1 and 5.2 of the protocol.

5.6.2. Deviations Assessed Post-Randomization

A full list of protocol deviations for the study report will be compiled prior to database closure. Any significant deviation from the protocol will be reviewed prior to database closure and a decision taken regarding evaluation for each analysis population.

6. ENDPOINTS AND COVARIATES

6.1. Efficacy Endpoint(s)

None.

6.2. Safety Endpoints

Any events occurring following start of treatment or increasing in severity will be counted as treatment emergent.

Events that occur in a non-treatment period (for example, Washout or Follow-up) will be counted as treatment emergent and attributed to the previous treatment taken.

The following data are considered in standard safety assessments (see protocol for collection days and list of parameters):

- *adverse events,*
- *laboratory data,*
- *vital signs data,*
- *ECG results.*

6.3. Other Endpoints

6.3.1. PK Endpoints

Blood samples for PK analysis of PF-07321332 will be taken according to the Schedule of Activities given in the protocol.

The following PK parameters will be calculated for PF-07321332 (if possible) from the concentration-time data using standard noncompartmental methods:

Table 3. Noncompartmental PK Parameters

PK Parameter	Analysis Scale	PF-07321332
AUC_{last}	ln	A, D
AUC_{inf}^*	ln	A, D
C_{max}	ln	A, D
C_{12}	R	D
C_{24}	R	D
T_{max}	R	D
$t_{1/2}^*$	R	D
CL/F^*	R	D
V_z/F^*	R	D

Key: A=analyzed using statistical model, D=displayed with descriptive statistics,
ln=natural-log transformed, R=raw (untransformed), *=if data permits.

If urine samples are need to be analyzed, the following urine PK parameters (Table 4) will be calculated for PF-07321332 (as data permit):

Table 4. Urine PK Parameters

PK Parameter	Analysis Scale	PF-07321332
Ae ₄₈	R	D
Ae ₄₈ %	R	D
CL _r	R	D

Key: D=displayed with descriptive statistics, R=raw (untransformed).

6.3.2. PD Endpoints

None.

6.4. Covariates

None.

7. HANDLING OF MISSING VALUES

For the analysis of safety endpoints, the sponsor data standard rules for imputation will be applied.

7.1. Concentrations Below the Limit of Quantification

In all data presentations (except listings), concentrations below the limit of quantification (BLQ) will be set to zero. (In listings BLQ values will be reported as “<LLQ”, where LLQ will be replaced with the value for the lower limit of quantification.)

7.2. Deviations, Missing Concentrations and Anomalous Values

In summary tables and plots of median profiles, statistics will be calculated having set concentrations to missing if 1 of the following cases is true:

1. A concentration has been collected as ND (ie, not done) or NS (ie, no sample).
2. A deviation in sampling time is of sufficient concern or a concentration has been flagged anomalous by the pharmacokineticist.

Note that summary statistics will not be presented at a particular time point if more than 50% of the data are missing.

7.3. Pharmacokinetic Parameters

Actual PK sampling times will be used in the derivation of PK parameters.

If a PK parameter cannot be derived from a participant's concentration data, the parameter will be coded as NC (ie, not calculated). (Note that NC values will not be generated beyond the day that a participant discontinues).

In summary tables, statistics will be calculated by setting NC values to missing; and statistics will be presented for a particular treatment with ≥ 3 evaluable measurements. For statistical analyses (ie, analysis of variance), PK parameters coded as NC will also be set to missing; and analyses will not be performed for a particular parameter if more than 50% of the data are NC.

If an individual participant has a known biased estimate of a PK parameter (due for example to an unexpected event such as vomiting before all the compound is adequately absorbed in the body), this will be footnoted in summary tables and will not be included in the calculation of summary statistics or statistical analyses.

8. STATISTICAL METHODOLOGY AND STATISTICAL ANALYSES

8.1. Statistical Methods

8.2. Statistical Analyses

ANOVA will be used to compare the natural log transformed AUC_{inf} (or AUC_{last} if AUC_{inf} cannot be reliably estimated) and C_{max} for PF-07321332 between normal renal function group (Reference) and each impaired renal function group separately as applicable (Test). Estimates of the adjusted mean differences (Test-Reference) and corresponding 90% CIs will be obtained from the model. The adjusted mean differences and 90% CIs for the differences will be exponentiated to provide estimates of the ratio of the adjusted geometric means (Test/Reference) and 90% CIs for the ratios. If substantial differences in demographic characteristics between healthy and impaired participants are observed, weight and age may be explored as covariates.

Box and whisker plots for individual participant parameters (AUC_{inf} and C_{max}) will be constructed by renal function group and overlaid with geometric means.

For summary statistics and median/mean plots by sampling time, the nominal PK sampling time will be used. For individual participant plots by time, the actual PK sampling time will be used.

Linear regression will be used to analyze the potential relationship between appropriate PK parameters (CL/F or CL_r , and V_z/F) and renal function (eGFR). Estimates of the slope and, intercept, together with their precision (90% CI), and the coefficient of determination will be obtained from the model.

Plots of PK parameters (CL/F or CL_r , and V_z/F) versus renal function (eGFR) will be constructed. A regression line and 90% confidence region for the PK parameters and eGFR will be included if appropriate. Vertical lines for the renal function group cut-off values will also be presented on the plots. Different symbols will be used to identify participants from different renal function groups.

Residuals from the model will be examined for normality and the presence of outliers via visual inspection of plots of residuals vs predicted values and normal probability plots of residuals but these will not be included in the clinical study report. If there are major deviations from normality or outliers then the effect of these on the conclusions will be investigated through alternative transformations and/or analyses excluding outliers. Justification for any alternative to the planned analysis will be given in the report of the study.

Table 5. PK Parameters to be Summarized Descriptively by Cohort

Parameter	Summary Statistics
AUC _{inf} , AUC _{last} , C _{max} , C ₁₂ , C ₂₄ , t _{1/2} , CL/F, V _z /F	N, arithmetic mean, median, cv%, standard deviation, minimum, maximum, geometric mean and geometric cv%.
t _{1/2}	N, arithmetic mean, median, cv%, standard deviation, minimum, maximum.
T _{max}	N, median, minimum, maximum.

Supporting data from the estimation of t_{1/2}, AUC_{inf} will be listed by Cohort: terminal phase rate constant (k_{el}); goodness of fit statistic from the log-linear regression (r²); the percent of AUC_{inf} based on extrapolation (AUC_{extrap%}); and the first, last, and number of time points used in the estimation of k_{el}. This data may be included in the clinical study report.

Presentations for PF-07321332 concentrations will include:

- A listing of all concentrations sorted by participant ID, period and nominal time postdose. The concentration listing will also include the actual times. Deviations from the nominal time will be given in a separate listing.
- A summary of concentrations by cohort and nominal time postdose, where the set of statistics will include n, mean, median, standard deviation, coefficient of variation (cv), minimum, maximum and the number of concentrations above the lower limit of quantification.
- Median concentrations time plots (on both linear and semi-log scales) against nominal time postdose by cohort (all cohorts on the same plot per scale, based on the summary of concentrations by cohort and time postdose).
- Mean concentrations time plots (on both linear and semi-log scales) against nominal time postdose by cohort (all cohorts on the same plot per scale, based on the summary of concentrations by cohort and time postdose).
- Individual concentration time plots by cohort (on both linear and semi-log scales) against actual time postdose (there will be separate spaghetti plots for each cohort per scale).

- A listing of all urine concentration intervals sorted by renal function group (present in heading), participant ID and nominal collection duration postdose.

For summary statistics, median and mean plots by sampling time, the nominal PK sampling time will be used, for individual participant plots by time, the actual PK sampling time will be used.

8.3. Safety Analysis

A set of summary tables split by cohort will be produced to evaluate any potential risk associated with the safety and toleration of administering study treatments.

8.3.1. Treatment and Disposition of Participants

Participant evaluation groups will show end of study participant disposition and will show which participants were analyzed for pharmacokinetics, as well as for safety (adverse events and laboratory data). Frequency counts will be supplied for participant discontinuation(s) by cohort.

Data will be reported in accordance with the sponsor reporting standards.

8.3.2. Demographic and Clinical Examination Data

A breakdown of demographic data will be provided for age, race, weight, body mass index, and height. Each will be summarized by sex at birth and 'All Participants' in accordance with the sponsor reporting standards.

8.3.3. Discontinuation(s)

Participant discontinuations, temporary discontinuations or dose reductions due to adverse events will be detailed and summarized by cohort.

Data will be reported in accordance with the sponsor reporting standards.

8.3.4. Adverse Events

Adverse events will be reported in accordance with the sponsor reporting standards by cohort.

8.3.5. Laboratory Data

Laboratory data will be listed in accordance with the sponsor reporting standards.

8.3.6. Vital Signs Data

Supine blood pressure, pulse rate, respiratory rate and oral temperature will be measured at the protocol specified timepoints.

These data will be listed in accordance with the sponsor reporting standards.

8.3.7. ECG Data

ECG data will be listed in accordance with the sponsor reporting standards.

8.3.8. Other Safety Data

None.

8.3.9. Concomitant Treatments

All concomitant medication(s) as well as non-drug treatment(s) will be provided in the listings.

8.3.10. Screening and Other Special Purpose Data

The screening data with the exception of demography and lab creatine data will not be brought in-house, and therefore will not be listed.

CCI

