1.3. Schedule of Activities

The SoA table provides an overview of the protocol visits and procedures. Refer to the **STUDY ASSESSMENTS AND PROCEDURES** section of the protocol for detailed information on each procedure and assessment required for compliance with the protocol.

The investigator may schedule visits (unplanned visits) in addition to those listed in the SoA table, in order to conduct evaluations or assessments required to protect the well-being of the participant.

Visit Identifier ^a	Screening ^b		Day -1 ^b	Day 1	Day 2	Day 3	Follow-up Contact	Early Termination/ Discontinuation (DC)
	Day -28 to Day -2							
Days Relative to Day 1 Abbreviations used in this table can be found in Appendix 9	S1	S2						
Informed consent	X							
Admission to CRU			X					
Confinement to CRU			X	→	→	X		
Inclusion/exclusion criteria	X		X					
Medical history	X		X					
Demography ^d	X							
Physical examination ^e	X		X			X		X
Height and weight assessment ^f	X	X	X				X ^g	
Safety laboratory tests (blood and urine) ^h	X	X ⁱ	X			X	X ^g	X
eGFR assessment ^j	X	X	X				X ^g	
Illegal drug/tobacco/alcohol use	X		X					
Urine alcohol test or alcohol breath test	X		X					
Urine or serum pregnancy test (WOCBP only)	X		X			X		X
Contraception check ^k	X	X	X			X	X	X
Serum FSH in post-menopausal females amenorrheic ≥ 12 months and under 60 years of age	X							
Urine drug screen	X		X					
Single supine 12-Lead ECG	X			X		X		X

PFIZER CONFIDENTIAL

Visit Identifier ^a	Screening ^b		Day -1 ^b	Day 1	Day 2	Day 3	Follow-up Contact	Early Termination/Discontinuation (DC)					
	Day -28 to Day -2												
	S1	S2					28-35 Days ^c						
Days Relative to Day 1 Abbreviations used in this table can be found in Appendix 9													
Vital signs (supine BP, respiratory rate, pulse rate) and temperature	X			X		X		X					
HIV, HBsAg, HBcAb, HCVAb testing ^d	X												
PF-07321332 administration				X									
Ritonavir administration ^e			X	X	X								
Plasma PK for PF-07321332				X	X	X		X					
Urine PK for PF-07321332				X	X	X							
CCI			■										
Prior/concomitant treatments	X	X	X	→	→	X	X	X					
COVID-19 testing ^o	X	X	X										
COVID-19 check temperature ^p	X	X	X	X	X	X							
COVID-19 questionnaire ^q			X										
CRU discharge						X							
Serious and nonserious adverse event monitoring	X	X	X	→	→	X	X	X					

- a. Day relative to start of PF-07321332 dosing (Day 1).

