j. To confirm eligibility, participants must have stable renal function defined as $\leq 25\%$ difference for eGFR values at S2 compared to the value at S1. The average of the 2 screening eGFR values will be used for participant stratification and group assignment (provided stable renal function is still demonstrated). If the renal function stability criterion is met but the renal function classification category changes between S1 eGFR and the average of the S1 and S2 eGFRs, the eGFR measurement at Day -1 will also be used to determine the appropriate group classification category using an average of all 3 eGFR values, to determine whether the participant will be eligible for enrollment. The Day -1 eGFR value will be used for PK analysis. The eGFR determination will utilize the 4-variable CKD-EPI method. A follow-up eGFR will be collected at Day 28 (with window of +3 days to allow for holidays) for any participant who demonstrates an increase of $>25\%$ in serum creatinine from Day -1 to Day of discharge. Serum creatinine laboratory test may be repeated once to confirm results at the discretion of the investigator; the last value will be used to calculate eGFR.

k. Confirmation of appropriate use only.

l. HBsAb will be performed as reflex testing for any participant who is HBsAg negative and HBcAb positive (Section 10.2). HCV RNA will be performed as reflex testing for any participant who is HCV Ab positive (Section 10.2).

m. Ritonavir will be administered on Day -1 at -12 hours, Day 1 at 0 hours and 12 hours, and Day 2 at 24 hours, relative to PF-07321332 dosing.

EE

o. Testing for COVID-19 pathogen by RT-PCR will be performed prior to being admitted to the clinic for confinement, on S1, S2, and Day -1 (only 1 test needed if S2 = Day -1), and if participant develops COVID-19 like symptoms.

p. To be done at least daily during residence. On days in which vitals are being collected, temperature will only need to be taken once and documented.

q. Check exposure to positive case, residence or travel in area of high incidence and COVID-19 related signs and symptoms.

Pharmacokinetic Sampling Schema

Study Day	-1	1										2	3	
Hours Before/After Dose	-12	0 ^a	0.5	1	2	3	4	6	8	10	12	24	36	48
PF-07321332 administration		X												
Ritonavir administration	X	X										X	X	
PK blood sampling ^b		X	X	X	X	X	X	X	X	X	X	X	X	X
PK urine collection ^c		X	→	→	→	→	→	→	→	→	→	X	→	X

a. Predose PF-07321332 and ritonavir sample collection.

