6. STUDY INTERVENTION(S) AND CONCOMITANT THERAPY

Study intervention is defined as any investigational intervention(s), marketed product(s), placebo, medical device(s), or study procedure(s) intended to be administered to a study participant according to the study protocol.

For the purposes of this protocol, study intervention refers to PF-07321332 and ritonavir.

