9.3.1. Other Safety Analyses

All safety analyses will be performed on the safety population.

AEs, ECGs, BP, pulse rate, and safety laboratory data will be reviewed and summarized on an ongoing basis during the study to evaluate the safety of participants. Any clinical laboratory, ECG, BP, and pulse rate abnormalities of potential clinical concern will be described. Safety data will be presented in tabular and/or graphical format and summarized descriptively, where appropriate.

Medical history and physical examination and neurological examination information, as applicable, collected during the course of the study will be considered source data and will not be required to be reported, unless otherwise noted. However, any untoward findings identified on physical and/or neurological examinations conducted during the active collection period will be captured as AEs, if those findings meet the definition of an AE. Data collected at screening that are used for inclusion/exclusion criteria, such as laboratory data, ECGs, and vital signs, will be considered source data, and will not be required to be reported, unless otherwise noted. Demographic data collected at screening will be reported.

CCI

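### The only scheduled pre-ritonavir ECG, blood pressure, pulse and respiratory rate are at the first screening visit, and the SAP leaves them out of the sponsor database, so change from an untreated baseline cannot be summarised

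*SAP*

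**What the plan says.** **Schedule.** In the Schedule of Activities (protocol 1.3), the rows "Single supine 12-Lead ECG" and "Vital signs (supine BP, respiratory rate, pulse rate) and temperature" are marked at S1, Day 1, Day 3 and early termination. The cells for S2, Day -1 and Day 2 are empty.

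**Dosing.** Footnote m of the same table states: "Ritonavir will be administered on Day -1 at -12 hours". Further doses follow at 0, 12 and 24 hours. Protocol section 6 adds that "study intervention refers to PF-07321332 and ritonavir".

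**Endpoint.** Protocol section 3 lists vital signs and ECGs among the secondary safety endpoints. The objective covers the safety and tolerability of both drugs.

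**Data handling.** SAP 8.3.10 excepts demography and what it calls lab creatine (presumably creatinine). All other screening data "will not be brought in-house, and therefore will not be listed". Protocol 9.3.1 takes the same position: screening ECGs and vital signs used for eligibility are source data that need not be reported unless noted otherwise.

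**Reporting.** SAP 8.3.7 reads: "ECG data will be listed in accordance with the sponsor reporting standards". SAP 8.3.6 treats vital signs in the same way. Neither section defines a baseline, a change from baseline or a summary table.

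**The concern.** There is no placebo or ritonavir-free arm, so a participant's own pre-ritonavir reading is the only internal reference for an effect of ritonavir or of the combination on QTcF, PR, blood pressure or pulse.

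The cohorts also differ at entry by design. Protocol 5.2.1 excludes QTcF above 450 msec in participants with normal renal function and above 470 msec in those with impairment. For blood pressure, 5.2.2 excludes healthy participants above 140/90 mm Hg, while 5.2.3 excludes impaired participants only from 180/110 mm Hg. A comparison of on-treatment values across cohorts mixes these entry differences with any drug effect. Change from an untreated value would help to separate them.

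The protocol's own criteria need a baseline as well. Section 8.2.3 uses a QTcF rise of at least 30 msec, and Appendix 7 a rise of at least 60 msec. Section 9.3.1 undertakes to describe ECG, blood pressure and pulse abnormalities of potential clinical concern.

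**Working it through.** The plan states no figure on this point. The check is a count of scheduled readings against the dosing times and the data rule.

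**1. Is any Day 1 reading untreated?** Protocol 6.1.1 puts PF-07321332 at about 0800 on Day 1, plus or minus 2 hours, so between 0600 and 1000. The first ritonavir dose is 12 hours earlier, between 1800 and 2200 on Day -1. Any reading dated Day 1 therefore follows ritonavir by at least 2 hours, even at the latest permitted dosing time.

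**2. Count for ECG, blood pressure, pulse rate and respiratory rate, per completer.**

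| Visit | Scheduled | Before ritonavir | In-house under SAP 8.3.10 | Both |
|---|---|---|---|---|
| S1 | 1 | 1 | 0 | 0 |
| Day 1 | 1 | 0 | 1 | 0 |
| Day 3 | 1 | 0 | 1 | 0 |
| Total | 3 | 1 | 2 | 0 |

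The same holds for every cohort, so none of the roughly 36 participants planned in the protocol would have a scheduled untreated value of these measures in the database.

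**3. What can be computed from the two retained readings?**
- Absolute limits can be applied: QT of 500 msec or more in 8.2.3, and QTcF above 480 msec in Appendix 7.
- Rises of 30 or 60 msec from an untreated value cannot.
- The change from Day 1 to Day 3 can be computed, but both ends are on ritonavir. The schedule does not say whether the Day 1 reading comes before PF-07321332. If it does, it is a baseline for PF-07321332 added to ritonavir. If not, it is a baseline for neither drug.

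**4. Which safety measures fall outside the problem?**
- Laboratory tests are scheduled on Day -1 and Day 3. Protocol 4.1 places the Day -1 safety assessments before dosing, so a pre-treatment value is available.
- Temperature is also taken on Day -1 as a COVID-19 check, at a time relative to ritonavir that is not stated.

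**5. Does the text elsewhere supply a Day -1 ECG or vital signs?** The synopsis and protocol 4.1 speak of safety assessments on Day -1. Section 4.1 defers to the Schedule of Activities, which on that day has a physical examination and laboratory tests but no ECG or vital signs.

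**The case against.** The strongest reply is that this is a deliberate choice made consistently in both documents. Protocol 9.3.1 treats screening ECGs and vital signs as source data, and SAP 8.3.10 carries that out. Individual safety does not depend on the database: site staff compare ECGs with baseline under 8.2.3, and clinically significant changes become adverse events, which are reported by cohort. This stands as far as individual protection goes. It gives no cohort-level summary of change, and 9.3.1 leaves room for exceptions to be noted.

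A second reply is that SAP 8.3 promises summary tables by cohort, and that the sponsor reporting standards, which are not among the documents, may add ECG and vital-sign tables. That is possible. Such tables would still have no scheduled untreated value to use.

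A third reply is that the gain is modest. The study tests no hypothesis, takes single ECGs and has about 8 participants per cohort. Day 3 is 48 hours after PF-07321332 and 48 - 24 = 24 hours after the last ritonavir dose, so a change from S1 to Day 3 may miss a peak effect. This stands, and it limits the weight of the point.

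A reader might also infer more than the documents support:
- **That the SAP contradicts the protocol by listing these data.** Protocol 9.3.1 does say "Safety data will be presented in tabular and/or graphical format and summarized descriptively", but the sentence goes on to limit this to where it is appropriate. Listing is compatible with it.
- **That laboratory data have the same gap.** SAP 8.3.5 says "Laboratory data will be listed in accordance with the sponsor reporting standards", but the Day -1 value is there for anyone who wants a change.
- **That the S1 readings are thrown away.** They remain in the site's source records.
- **That the cohorts cannot be compared at all.** Day 1 and Day 3 values are kept, and the ritonavir regimen is the same in every cohort.

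**Conclusion.** The point holds for ECG, blood pressure, pulse rate and respiratory rate. Of 3 scheduled readings per completer, 1 is untreated and it is the one left out of the sponsor database. Followed as written, the plan cannot give change from an untreated baseline, or apply its own QTcF-change criteria from its own data, for the effect of ritonavir or the combination. It applies only partly to temperature and not to laboratory tests.

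This rests on reading the Schedule of Activities as printed, with no ECG or vital signs on Day -1, and on no unscheduled pre-dose reading being entered in the database. The consequence is confined to a descriptive secondary safety endpoint. The primary PK analysis is unaffected. The change is worth making because the value is already collected and costs little to use.

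**What to change.** 1. In SAP 8.3.10, add the S1 ECG and vital signs to the screening data brought in-house, and record this as an exception under protocol 9.3.1.
2. Define baseline for ECG and vital signs as the last value before the first ritonavir dose.
3. In SAP 8.3.6 and 8.3.7, add descriptive summaries by cohort of observed values and of change from that baseline.
4. State whether the Day 1 reading is taken before PF-07321332. If it is, show it as a second reference, labelled as a baseline for PF-07321332 added to ritonavir.

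The cost is data entry for values already measured and a few standard tables, with no new procedure for participants. The weakness is the quality of the baseline: one outpatient reading that may be 28 days old, or older where protocol section 8 allows dosing beyond 28 days without rescreening. With about 8 participants per cohort, the summaries should be read as descriptive only.
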